3 STUDY PURPOSE AND OBJECTIVES

This study is an open-label, dose escalation, Phase 1b/2 study designed to characterize the safety, tolerability, PK, pharmacodynamics (PD), immunogenicity, and preliminary antitumor activity of margetuximab administered IV once every 3 weeks in combination with 200 mg pembrolizumab administered IV once every 3 weeks in patients with relapsed/refractory unresectable locally advanced or metastatic HER2+ GEJ or GC.

3.1 Primary Objectives

The primary objectives of this study are:

- To characterize the safety, tolerability, DLT, and MTD or MAD (if no MTD is defined) of margetuximab when administered IV every 3 weeks in combination with 200 mg pembrolizumab administered IV every 3 weeks to patients with relapsed/refractory advanced HER2+ GEJ or GC.
- To investigate the preliminary anti-tumor activity, as measured by objective response rate (ORR) and response duration, of margetuximab administered IV every 3 weeks in combination with pembrolizumab administered IV every 3 weeks using both conventional Response Evaluation Criteria in Solid Tumors (RECIST) 1.1 ([Appendix 7](#)) and immune-related response criteria (irRC) ([Appendix 8](#)), in patients that have failed first-line trastuzumab-containing regimens.

3.2 Secondary Objectives

Secondary objectives of this study are:

- To investigate the preliminary effect on OS and PFS of margetuximab administered IV every 3 weeks in combination with pembrolizumab administered IV every 3 weeks
- To characterize the PD activity of margetuximab administered IV every 3 weeks in combination with pembrolizumab administered IV every 3 weeks.
- To characterize the PK and immunogenicity of margetuximab administered IV every 3 weeks in combination with pembrolizumab administered IV every 3 weeks.

3.3 Exploratory Objectives

- To explore the relationships between PK, PD, patient safety and antitumor activity of margetuximab when administered in combination with pembrolizumab.
- To investigate the immune-regulatory activity of margetuximab in combination with pembrolizumab by analysis of peripheral blood samples for potentiation of HER2 specific adaptive humoral and cellular immune responses.

- To determine the relationships between membranous expression of PD-L1 on tumor cells, immune cell infiltration within biopsy specimens (including but not limited to CD4+ and CD8+ T cells), PD-L1 expression on the immune cell infiltrate, and clinical response via IHC staining of paired pre- and on-treatment tumor biopsy specimens.
- To determine the relationship of allelic variation in *CD16A*, *CD32A* and *CD32B* to anti-tumor activity.
- Determination of mutational burden (on ctDNA determined by Guardant 360 assay), as well as mismatch repair status by microsatellite instability (from pathology reports, when available).
- To determine of gene expression signatures in tissues, which may be indicative of immunotherapy responses associated with the agents on trial.
- To validate ctDNA *ERBB2*, determined by circulating tumor DNA Guardant 360 assay amplification as a surrogate of HER2 expression in patients with GC; to be performed at Guardant Laboratories.

The results of exploratory objectives may not be included in the Clinical Study Report or final data tables and listings unless they represent meaningful findings.

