## **6.10 Subgroup Analysis**

Efficacy analyses will be performed by race (Asian vs Non-Asian), tumor location (GC vs GEJ), and other demographics and baseline characteristics. The analyses will also be performed by baseline biomarkers such as HER2 IHC status (IHC3+ vs IHC2+), PD-L1 status (PD-L1+ vs PD-L1-), double positive status (HER2 IHC3+ and PD-L1+ vs others), and by alleles coding for CD16A (VV, FF, FV, and FF and FV combined [F Carrier]), respectively.

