## **7 LIST OF TABLES, LISTINGS, AND FIGURES**

The list of tables, listings, and figures (TLFs) and associated shells planned for the clinical study report based on the analyses described in this SAP will be provided in a separate statistical programming plan (SPP), which will also include data reporting conventions and programming specifications for the development of these TLFs.

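### Protocol 3.3 lets exploratory results be left out of the study report unless they are undefined meaningful findings, which conflicts with the SAP for the CD16A subgroup and, in part, the PD-L1 subgroup

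*Protocol*

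**What the plan says.** Protocol 3.3 lists the exploratory objectives. They include the relation of Fc receptor alleles (CD16A, CD32A, CD32B) to anti-tumor activity, the relation of PD-L1 and immune infiltrate to clinical response, mutational burden and mismatch repair status, gene expression signatures, and validation of ctDNA ERBB2 as a surrogate for HER2 expression. The section closes with a reporting rule: these results "may not be included in the Clinical Study Report or final data tables and listings unless they represent meaningful findings".

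SAP 6.10 attaches no such condition. It says "The analyses will also be performed by baseline biomarkers such as HER2 IHC status", and goes on to name PD-L1 status, double-positive status (HER2 IHC3+ and PD-L1+) and CD16A alleles. SAP 7 describes the tables, listings and figures as "planned for the clinical study report based on the analyses described in this SAP", again with no filter on results. It leaves the actual list to a separate statistical programming plan.

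**The concern.** A rule that looks at the result before deciding whether to report it is selective reporting by design. The wording can be read in two ways. If it means must not, null results are barred. If it means might not, they can be dropped at discretion. Either way a reader of the study report would see the associations someone judged meaningful, without knowing how many were examined.

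Two items show what could be lost. Protocol 2.3.1 describes margetuximab as engineered for stronger binding to CD16A, and Protocol 2.1.2 cites longer PFS on trastuzumab by CD16A allele in metastatic breast cancer. A null CD16A result here would therefore be informative. The ctDNA ERBB2 objective is stated as a validation, and a validation that is reported only when it succeeds tells the reader little.

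**Working it through.** The plan has no figure to reproduce here. The check is to match each exploratory objective in Protocol 3.3 with the biomarker subgroups named in SAP 6.10, and to look in both documents for a definition of a meaningful finding. There is none.

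| Item | In Protocol 3.3? | Named in SAP 6.10? | Result |
|---|---|---|---|
| CD16A alleles against activity | Yes | Yes (VV, FF, FV, F carrier) | Direct conflict |
| PD-L1 against response | Yes, on paired pre- and on-treatment biopsies | Yes, as baseline status | Partial conflict |
| HER2 IHC 3+ against 2+ | No | Yes | Rule does not reach it |
| Double positive (HER2 IHC3+ and PD-L1+) | No | Yes | Rule does not reach it |
| CD32A and CD32B alleles against activity | Yes | No | Rule applies, no 6.10 commitment |
| Immune infiltrate against response | Yes | No | Rule applies, no 6.10 commitment |
| ctDNA ERBB2 validation | Yes | No | Rule applies, no 6.10 commitment |
| Mutational burden, gene signatures | Yes, as determinations only | No | Rule applies to any analysis against outcome |

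- **CD16A.** The objective begins "To determine the relationship of allelic variation in" the three receptor genes. SAP 6.10 plans efficacy by CD16A allele. For a null result the protocol permits omission, while SAP 6.10 and 7 together imply inclusion.
- **PD-L1.** The objective begins "To determine the relationships between membranous expression of PD-L1 on tumor cells, immune cell infiltration within biopsy specimens" and is framed on paired biopsies. SAP 6.10 uses baseline status, so the two overlap without being the same analysis.
- **HER2.** The nearest objective concerns ERBB2 "amplification as a surrogate of HER2 expression in patients with GC". That is an assay validation, not efficacy by IHC level.

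Of the four biomarker subgroups named in SAP 6.10, one is directly under the rule, one is partly under it, and two are outside it (1 + 1 + 2 = 4). SAP 6.10 introduces its list as examples, so other markers could be added, but nothing commits the sponsor to add them. SAP 2 lists only primary and secondary objectives, so the exploratory objectives have no section of their own in the SAP.

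**The case against.** The best reply is that much of this is handled elsewhere. SAP 6.10 says the biomarker analyses will be done, and SAP 7 builds the report's tables from the SAP. Protocol 7.7.1 says central HER2 and PD-L1 results will be used in efficacy analyses. Pharmacodynamic activity is a secondary objective, and Protocol 9.6 and SAP 6.8 say the parameters in Protocol 7.10.4 will be summarized. Those parameters include Fc genotype, PD-L1, T-cell infiltration, mutational burden and gene signatures. The study is mainly descriptive, and exploratory assays often finish late.

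Part of this stands. The markers themselves should be summarized, and a sponsor that follows the SAP would tabulate CD16A and PD-L1. But Protocol 9.6 and SAP 6.8 cover the parameters and their change from baseline, not their association with response, so they do not undo the rule in 3.3. Late assays justify an exception on timing, not on results. A descriptive study has more reason to show every description, because no multiplicity control stands behind those selected.

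A reader might go further than the documents allow in three ways:

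- **That the rule governs all the biomarker subgroups in SAP 6.10.** It governs only results of the 3.3 objectives, and HER2 IHC and double-positive status are not among them.
- **That 3.3 plans mutational burden and gene signatures against response.** It plans only their determination, and describes the signatures as possibly indicative of response.
- **That the false-positive risk can be quantified.** With 20 independent null tests at 5%, the chance of at least one nominal finding is 1 − 0.95^20 = 64%; with 40 it is 1 − 0.95^40 = 87%. But neither document states a test or an alpha for these analyses, or how many there will be. The endpoints are correlated, and meaningful need not mean p < 0.05. A figure for inflated effect sizes would also need an assumed response rate and subgroup split.

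**Conclusion.** The concern holds in a limited form. Protocol 3.3 states a results-dependent reporting rule with no criterion and no one named to apply it. It is unreconciled with SAP 6.10 and 7 for CD16A and, in part, for PD-L1. It stands without a competing SAP 6.10 commitment for the exploratory associations listed above that 6.10 does not name. This conclusion rests on the text alone and holds under either reading of the wording.

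The direction of the bias is clear: what is shown would be selected toward apparent associations. Its size cannot be computed from the documents. Nor can it be said what the study report will omit, because the table list is in a programming plan not available here. The rule does not touch the primary or secondary objectives, so this is a matter of reporting integrity for the biomarker work, not of the trial's main conclusions.

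**What to change.** Delete the closing sentence of Protocol 3.3 and replace it with:

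> All exploratory analyses that are run will be reported, whatever the result, in the CSR or a dated addendum, with the number of markers and endpoints examined. Planned analyses not run will be listed with the reason.

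State in SAP 6.10 that every named biomarker subgroup is tabulated.

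The cost is one protocol sentence and one SAP sentence, plus a few appendix tables or a later addendum for assays that finish late. No patient procedure or sample size changes.

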4 TRIAL DESIGN

4.1 Overall Study Design and Plan

4.1.1 General Study Design

This study is a Phase 1b/2, open-label, dose escalation and cohort expansion study designed to characterize the safety, tolerability, PK, PD, immunogenicity, and preliminary antitumor activity of margetuximab administered IV every 3 weeks in combination with pembrolizumab administered IV every 3 weeks in patients with relapsed/refractory, unresectable locally advanced or metastatic HER2+ GEJ or GC.

The study consists of a **Dose Escalation Phase (Part A)** to determine the MTD or MAD (if no MTD is defined) of escalating doses of margetuximab administered in combination with a fixed dose of 200 mg pembrolizumab, followed by a **Cohort Expansion Phase (Parts B – C)** to further define the safety and initial efficacy of the combination with the margetuximab dose established in the first phase. As of Protocol Amendment 2, up to 25 additional patients with GC only will be added to Cohort Expansion Phase (Part C). See [Section 4.1.3](#).

Both margetuximab and pembrolizumab will be administered once every 3 weeks (one cycle). Both agents will be administered on the same day, with pembrolizumab administered first, followed by margetuximab. Each cycle of therapy is defined as 3 weeks, in which margetuximab and pembrolizumab will be given on Day 1. Tumor assessments will be performed every 6 weeks (i.e., following 2 cycles of treatment [prior to dosing for Cycles 3, 5, 7, etc.]) for the first 6 months on treatment; thereafter, tumor assessments will be performed every 12 weeks.

Assuming the patient remains clinically stable, has not experienced immune-related progressive disease (irPD), and does not experience unacceptable toxicity that necessitates permanent discontinuation of both study drugs, treatment with the combination treatment may continue for up to 2 years ([Section 4.4](#) and [Section 5.3](#)). Combination therapy with pembrolizumab and margetuximab will be discontinued after 2 years.

For patients who are otherwise clinically stable but have met conventional criteria for PD, therapy may be continued at the discretion of the investigator pending confirmation of progression at the next scheduled tumor assessment. This approach allows for limited treatment of patients beyond the initial radiographic documentation of disease progression, assuming that patients are tolerating therapy adequately, that patients remain otherwise clinically stable despite this initial radiographic evidence of disease progression, and that the investigator feels the patient may still derive benefit from continuation of therapy.

For patients in whom progression is confirmed at the next scheduled tumor assessment, the criteria for irPD will have been met, and treatment with margetuximab and pembrolizumab should be discontinued. The patient should be removed from study participation after completion of protocol specified follow-up (see [Section 8.3](#) and [Appendix 1](#) and [Appendix 2](#)).

Efficacy Follow-up Period: Following the last dose of combination therapy, all patients will be followed for PFS and OS for up to 2 years or until 3 months after the last patient completes or discontinues study treatment.

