For patients who demonstrate acceptable tolerability of treatment with pembrolizumab and margetuximab and achieve an objective response assessment of irCR, irPR or irSD, or unconfirmed clinically stable irPD, therapy may be continued (see [Section 4.4](#) and [Section 5.3](#)).

For patients who are otherwise clinically stable, but have met conventional criteria for PD, therapy may be continued at the discretion of the investigator pending confirmation of progression at the next scheduled tumor assessment. This approach allows for limited treatment of patients beyond the initial radiographic documentation of disease progression, assuming that patients are tolerating therapy adequately, that patients remain otherwise clinically stable despite this initial radiographic evidence of disease progression and that the investigator feels the patient may still derive benefit from continuation of therapy. Treatment of patients according to irRC principles is supported by well-documented evidence that in some patients treated with T cell directed, immune-modulatory agents, their tumors can evolve to an objective response after an initial period characterized by either apparent radiographic growth of target lesions or the development of new target lesions that would otherwise meet the criteria for disease progression using conventional response criteria ([Appendix 7](#)). In the context of the statistical analysis for this trial, objective response determination and the assessment of best overall response (BOR) will be defined using both conventional RECIST 1.1 ([Appendix 7](#)) as well as an adaptation of these criteria, designated as immune-related response criteria (irRC) ([Appendix 8](#)). Patient management decisions, however, will be made solely based on the immune-related response criteria ([Appendix 8](#)).

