For patients who are otherwise clinically stable, but have met conventional criteria for PD, therapy may be continued at the discretion of the investigator pending confirmation of progression at the next scheduled tumor assessment. This approach allows for limited treatment of patients beyond the initial radiographic documentation of disease progression, assuming that patients are tolerating therapy adequately, that patients remain otherwise clinically stable despite this initial radiographic evidence of disease progression, and that the investigator feels the patient may still derive benefit from continuation of therapy. Treatment of patients according to irRC principles is supported by well-documented evidence that in some patients treated with T cell directed, immune-modulatory agents, their tumors can evolve to an objective response after an initial period characterized by either apparent radiographic growth of target lesions or the development of new target lesions that would otherwise meet the criteria for disease progression using conventional response criteria ([Appendix 7](#)).

For patients in whom progression is confirmed at the next scheduled tumor assessment, the criteria for immune-related PD (irPD) will have been met, and treatment with margetuximab and pembrolizumab should be discontinued. The patient should be removed from study participation after completion of protocol specified follow-up (see [Section 8.3](#) and [Appendix 1](#) and [Appendix 2](#)). For patients who experience an objective response of immune-related complete response (irCR) or immune-related partial response (irPR), responses will be considered unconfirmed until the response has been documented by a subsequent confirmatory scan obtained no less than 4 weeks after the initial scan demonstrating an objective response.

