All other lesions (or sites of disease) including pathological lymph nodes should be identified as *non-target lesions* and should also be recorded at baseline. Measurements are not required and these lesions should be followed as ‘present’, ‘absent’, or in rare cases ‘unequivocal progression. In addition, it is possible to record multiple non-target lesions involving the same organ as a single item on the case record form (e.g. ‘multiple enlarged pelvic lymph nodes’ or ‘multiple liver metastases’).

RESPONSE CRITERIA

This section provides the definitions of the criteria used to determine objective tumor response for target lesions.

Evaluation of target lesions

Complete Response (CR): Disappearance of all target lesions. Any pathological lymph nodes (whether target or non-target) must have reduction in short axis to < 10 mm.

Partial Response (PR): at least a 30% decrease in the sum of diameters of target lesions, taking as reference the baseline sum diameters.

Progressive Disease (PD): at least a 20% increase in the sum of diameters of target lesions, taking as reference the *smallest sum on study* (this includes the baseline sum if that is the smallest on study). In addition to the relative increase of 20%, the sum must also demonstrate an absolute increase of at least 5 mm. (*Note*: the appearance of one or more new lesions is also considered progression).

Stable Disease (SD): Neither sufficient shrinkage to qualify for PR nor sufficient increase to qualify for PD, taking as reference the smallest sum diameters while on study.

Special notes on the assessment of target lesions

Lymph nodes. Lymph nodes identified as target lesions should always have the actual short axis measurement recorded (measured in the same anatomical plane as the baseline examination), even if the nodes regress to below 10 mm on study. This means that when lymph nodes are included as target lesions, the ‘sum’ of lesions may not be zero even if complete response criteria are met, since a normal lymph node is defined as having a short axis of <10 mm. In order to qualify for CR, each node must achieve a short axis <10 mm. For PR, SD and PD, the actual short axis measurement of the nodes is to be included in the sum of target lesions.

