Appendix 8 Immune-Related RECIST Guidelines

[Adapted from Wolchok 2009 (82)]

All patients will be required to have at least 1 measurable lesion to be considered as having measurable disease at baseline for the determination of eligibility for this study. Measurable lesions are defined below.

MEASURABILITY OF TUMOR AT BASELINE

DEFINITIONS

At baseline, tumor lesions/lymph nodes will be categorized measurable or non-measurable as follows:

Measurable

Tumor lesions: Must be accurately measured in at least one dimension (*longest* diameter in the plane of measurement is to be recorded) with a *minimum* size of:

- 10 mm by CT scan (CT scan slice thickness no greater than 5 mm).
- 10 mm caliper measurement by clinical exam (lesions which cannot be accurately measured with calipers should be recorded as non-measurable).
- 20 mm by chest X-ray.

Malignant lymph nodes: To be considered pathologically enlarged and measurable, a lymph node must be ≥ 15 mm in *short* axis when assessed by CT scan (CT scan slice thickness no greater than 5 mm). At baseline and in follow-up, only the *short* axis will be measured and followed. See also notes below on ‘Baseline documentation of target and non-target lesions’ for information on lymph node measurement.

Non-measurable

All other lesions, including small lesions (longest diameter < 10 mm or pathological lymph nodes with ≥ 10 to < 15 mm short axis) as well as truly non-measurable lesions. Lesions considered truly non-measurable include: leptomeningeal disease, ascites, pleural or pericardial effusion, inflammatory breast disease, lymphangitic involvement of skin or lung, abdominal masses/abdominal organomegaly identified by physical exam that is not measurable by reproducible imaging techniques.

Special considerations regarding lesion measurability

Bone lesions, cystic lesions, and lesions previously treated with local therapy require particular comment:

Bone lesions:

- Bone scan, PET scan or plain films are not considered adequate imaging techniques to measure bone lesions. However, these techniques can be used to confirm the presence or disappearance of bone lesions.
- Lytic bone lesions or mixed lytic-blastic lesions, with identifiable soft tissue components, that can be evaluated by cross sectional imaging techniques such as CT or MRI can be considered as measurable lesions if the soft tissue component meets the definition of measurability described above.
- Blastic bone lesions are non-measurable.

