All other lesions (or sites of disease) including pathological lymph nodes should be identified as *non-target lesions* and should also be recorded at baseline. Measurements are not required and these lesions should be followed as ‘present’, ‘absent’, or in rare cases ‘unequivocal progression’. In addition, it is possible to record multiple non-target lesions involving the same organ as a single item on the case record form (e.g. ‘multiple enlarged pelvic lymph nodes’ or ‘multiple liver metastases’).

RESPONSE CRITERIA

This section provides the definitions of the criteria used to determine objective tumor response for target lesions by immune-related response criteria.

Evaluation of target lesions

Immune-Related Complete Response (irCR): Disappearance of all target lesions. Any pathological lymph nodes (whether target or non-target) must have reduction in short axis to <10 mm.

Immune-Related Partial Response (irPR): at least a 30% decrease in the sum of diameters of target lesions, taking as reference the baseline sum diameters.

Immune-related Progressive Disease (irPD): at least a 20% increase in the sum of diameters of target lesions, taking as reference the *smallest sum on study* (this includes the baseline sum if that is the smallest on study). In addition to the relative increase of 20%, the sum must also demonstrate an absolute increase of at least 5 mm.

Unlike conventional RECIST criteria, the appearance of new measurable lesions does not automatically denote disease progression under immune-related response criteria. Rather the dimensions of new measurable lesions are added to overall sum of tumor diameters for determination of objective response status. Patients will not be considered as having progression unless the new overall sum of diameters has increased by $\geq 20\%$ from the smallest sum of tumor diameters achieved while on study.

Immune-Related Stable Disease (irSD): Neither sufficient shrinkage to qualify for PR nor sufficient increase to qualify for PD, taking as reference the smallest sum diameters while on study.

Special notes on the assessment of target lesions

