Lesions that split or coalesce on treatment. When non-nodal lesions ‘fragment’, the longest diameters of the fragmented portions should be added together to calculate the target lesion sum. Similarly, as lesions coalesce, a plane between them may be maintained that would aid in obtaining maximal diameter measurements of each individual lesions. If the lesions have truly coalesced such that they are no longer separable, the vector of the longest diameter in this instance should be the maximal longest diameter for the ‘coalesced lesion’.

Evaluation of non-target lesions

This section provides the definitions of the criteria used to determine the tumor response for the group of non-target lesions. While some non-target lesions may actually be measurable, they need not be measured and instead should be assessed only *qualitatively* at the time points specified in the protocol.

Immune-Related Complete Response (irCR): Disappearance of all non-target lesions. All lymph nodes must be non-pathological in size (<10mm short axis).

Non-CR/Non-PD: Persistence of one or more non-target lesions(s).

Immune-Related Progressive Disease (irPD): Unlike conventional RECIST 1.1, new measurable lesions or increases in the size of non-target lesions do not define PD in isolation in the immune-related response criteria. Rather, immune-related PD is established if the sum of diameters is $\geq 20\%$ of the nadir of the sum of diameters for a given patient.

New Lesions

The appearance of new malignant lesions alone does not denote disease progression. Instead, the diameter of new lesions is added to the sum of diameters for target and non-target lesions.

EVALUATION OF BEST OVERALL RESPONSE

The best overall response is the best response recorded from the start of the study treatment until the end of treatment taking into account any requirement for confirmation. The patient’s best overall response assignment will depend on the findings of both target and non-target disease.

Time point response

It is assumed that at each protocol specified time point, a response assessment occurs. For patients experiencing irCR or irPR, a confirmatory scan obtained no less than 4 weeks after the original scan is required to confirm the objective response. For patients experiencing irPD, but who demonstrate acceptable tolerability of treatment as evaluated by the investigator, a confirmatory scan obtained no less than 4 weeks after the original scan is required for the confirmation of irPD.

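### Four sentences treat confirmed conventional progression as irPD and stop both drugs, but under Appendix 8 some of these patients are irSD or irPR and may continue

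*Protocol*

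**What the plan says.** The Synopsis (General Study Design and Efficacy Assessments), Section 4.1.1 and Section 7.10.1.1 share one sequence. They first describe clinically stable patients who "have met conventional criteria for PD, therapy may be continued at the discretion of the investigator pending confirmation of progression". They then state: "For patients in whom progression is confirmed at the next scheduled tumor assessment, the criteria for irPD will have been met" (Section 4.1.1; the two Synopsis places match). Section 7.10.1.1 has "For patients in whom progression is confirmed at the next scheduled tumor assessment, the criteria for immune-related PD (irPD) will have been met". In each place both drugs should then be discontinued, and the next sentence removes the patient from the study once follow-up is complete.

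The two sets of criteria define progression differently:

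- **Appendix 7 (RECIST 1.1):** besides growth of target lesions, "the appearance of one or more new lesions is also considered progression".
- **Appendix 8 (immune-related):** new measurable lesions are added to the sum, and "Patients will not be considered as having progression unless the new overall sum of diameters has increased by" at least 20% from the smallest sum on study. The target-lesion definition also requires an absolute rise of at least 5 mm. The non-target section adds that "new measurable lesions or increases in the size of non-target lesions do not define PD in isolation in the immune-related response criteria". For irPD in a patient tolerating treatment, "a confirmatory scan obtained no less than 4 weeks after the original scan is required for the confirmation of irPD". SAP 5.1.1 also requires irPD to be confirmed, at 28 days or more.

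Section 7.10.1.1 and the matching Synopsis text base management on the immune-related criteria alone. They allow patients with irCR, irPR, irSD or unconfirmed, clinically stable irPD to continue.

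**The concern.** In all four places the progression awaiting confirmation is conventional PD. The sentence then asserts that confirming it satisfies irPD. RECIST 1.1 PD can rest on a new lesion that Appendix 8 does not count as progression, so the inference fails for some patients.

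A site following these sentences would take both drugs away from a patient whom Section 7.10.1.1 allows to continue. Two sites relying on different parts of the protocol could treat identical scans differently. Response rate and duration by immune-related criteria are part of a primary objective. Appendix 8 records best overall response only to the end of treatment, so a wrong stop could lose a later irPR. Section 7.10.1.1 defends treatment beyond progression by pointing to patients who respond after new lesions appear, and those are the patients the next paragraph can stop.

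**Working it through.** There is no plan figure to reproduce. The check applies both sets of criteria to the same scans.

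**Inputs**
- RECIST 1.1 PD: any new lesion, or target sum at least 20% and 5 mm above nadir (Appendix 7).
- irPD: target plus new measurable sum at least 20% and 5 mm above nadir, with the nadir taken on that same total sum (Appendix 8, target-lesion section and response table).
- irPR: sum at least 30% below baseline; otherwise irSD.
- Smallest lesion measurable by CT: 10 mm; smallest measurable node: 15 mm short axis (Appendix 8).
- Scans every 6 weeks for the first 24 weeks, so consecutive scans are 42 days apart, more than the 28 required for confirmation.

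**Threshold.** With target lesions unchanged, a new lesion of d mm raises a nadir sum N by d/N. This is below 20% when N > d/0.20:
- d = 10 mm: N > 50 mm
- d = 15 mm: N > 75 mm
- d = 20 mm: N > 100 mm

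Each d exceeds 5 mm, so the 20% condition decides. Above these limits the patient has RECIST 1.1 PD but not irPD.

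**Constructed patients, baseline sum 100 mm** (sizes are assumptions; they show what can happen, not how often)

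| Patient | Week | Targets + new = sum (mm) | Change | RECIST 1.1 | Appendix 8 |
|---|---|---|---|---|---|
| 1 | 6 | 90 + 12 = 102 | +2% from nadir | PD | irSD |
| 1 | 12 | 90 + 14 = 104 | +4% from nadir | PD | irSD |
| 2 | 6 | 50 + 10 = 60 | -40% from baseline | PD | irPR |
| 2 | 12 | 45 + 12 = 57 | -43% from baseline | PD | irPR, confirmed |
| 3 | 6 | 125 + 0 = 125 | +25% from nadir | PD | irPD |
| 3 | 12 | 130 + 0 = 130 | +30% from nadir | PD | irPD, confirmed |
| 4 | 6 | 100 + 12 = 112 | +12% from nadir | PD | irSD |
| 4 | 12 | 110 + 15 = 125 | +25% from nadir | PD | irPD, first seen |

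The four sentences are right for patient 3. They are wrong for patients 1 and 2; patient 2 is a confirmed immune-related responder. Patient 4 shows a timing error. The second scan confirms RECIST 1.1 PD but is the first to show irPD, so irPD is unconfirmed and a clinically stable patient may continue.

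**How a response could be lost.** Sums at weeks 6, 12, 18 and 24: 88 + 12 = 100 (0%, irSD), 70 + 12 = 82 (-18%, irSD), 55 + 10 = 65 (-35%, irPR), 52 + 10 = 62 (-38%, irPR confirmed). If persistence of the new lesion counts as confirmation, the four sentences stop treatment at week 12, while best response is still irSD.

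**The case against.** The best defence is that confirmed progression was meant as progression confirmed under Appendix 8. That appendix is the main place where progression needs a confirmatory scan; Appendix 7 uses the idea only for equivocal findings. The Synopsis text on duration of treatment supports this, because it lists confirmation of PD and satisfaction of irPD together. The stopping lists (Synopsis and Section 4.4) use irPD per Appendix 8, and Section 5.3.1 uses progression by the immune-related criteria.

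This settles which rule was intended. It does not make the four sentences correct. On that reading they become circular and disregard their own starting point, a patient with conventional PD. A contrary stopping instruction still stands in four places.

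Other parts of the defence stand:
- A new lesion that merely persists while the total burden shrinks is arguably not confirmed progression, since no text defines the term. The last sequence above depends on this; patients 1 and 2, whose new lesion grows, do not.
- Continuation is permitted, not required, and investigator discretion is a separate ground for stopping (Section 4.4).

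A reader might infer that PD from non-target growth or from new non-measurable lesions is an equally clear case. The target-lesion section and response table of Appendix 8 support that. However, its New Lesions paragraph adds new lesions, without limiting them to measurable ones, to a sum over target and non-target lesions. On that wording these routes could contribute to irPD. Appendix 7 also calls PD solely from non-target change extremely rare when target disease is stable or responding.

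**Conclusion.** As written, the four sentences are false under Appendix 8. The clear case is RECIST 1.1 PD from new measurable lesions that leave the total sum less than 20% above nadir: for one new 10 mm lesion with unchanged targets, any nadir sum above 50 mm. This rests on reading the preceding paragraph as defining what is confirmed, and on taking the irPD sum as target plus new measurable lesions.

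The result is an internal contradiction in a stopping instruction. It does not leave the protocol without a correct stopping rule. Three stronger inferences are not supported:
- **That a material number of patients is affected.** The documents give no basis for a frequency.
- **That patients have been wrongly stopped.** Nothing in the documents shows this; sites may have followed the irPD rule.
- **That the main RECIST 1.1 results are compromised.** The RECIST 1.1 ORR criteria and the PFS definition do not change. The possible effect is on treatment duration and response by immune-related criteria.

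It should be corrected because it is an operative instruction that sites read, and correcting it is cheap.

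**What to change.** In all four places, replace both the sentence and the study-removal sentence that follows it. Suggested text:

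> Patients whose scan shows irCR, irPR, irSD, or unconfirmed clinically stable irPD remain under the continuation rule in Section 7.10.1.1. If irPD as defined in Appendix 8 is confirmed on a scan at least 4 weeks after the one that first showed irPD, both study drugs are stopped and the patient leaves the study once protocol-specified follow-up is complete.

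Both sentences must change together. Otherwise the removal instruction could come directly after patients who are allowed to continue. Refer to Appendix 8 for irPD and do not restate it in part: quoting the 20% rise alone would drop the 5 mm condition.

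The cost is two sentences replaced in four places. It needs no new data, visits or analyses, and no SAP change.
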